2.4.1.1 Duration of exposure to study treatment

The duration of exposure to study treatment will be calculated as:

Duration of exposure to study treatment (days) = **(last date of exposure** to any treatment component) – (date of first administration of study treatment component) + 1

The duration of exposure to any single component of study treatment will be calculated as:

Duration of exposure (days) = (last day of exposure to study treatment component) – (date of first administration of study treatment component) + 1

The **last date of exposure** is defined as follows for the study treatment component:

- For Lutathera, the last date of exposure is defined as the last date of administration + 55 days
- For Octreotide LAR, the rules are the following:
 - For patients randomized in the investigational arm, if the last date of administration occurs after an administration of Lutathera, the last date of exposure is defined as the last date of administration for Octreotide + 55 days
 - For patients randomized in the investigational arm, if the last date of administration occurs after the 6-week washout period of the last dose of Lutathera (i.e., Octreotide starts the every 4 weeks schedule after discontinuation of Lutathera), then the last date of exposure is defined as the last date of administration + 27 days
 - For patients randomized in the control arm, the last date of exposure is defined as the last date of administration + 27 days

This duration of exposure includes the periods of temporary interruption (of any component of the study treatment for any reason). The duration of study treatment exposure and exposure to each treatment component will be summarized by treatment group and by treatment period. In addition, number of cycles and average duration of cycle (for Lutathera only) will also be summarized for single component of study treatment by treatment period.

For analyses related to the cross-over/re-treatment period, duration of exposure to Lutathera will be calculated as above during either the cross-over or re-treatment period as appropriate. Since administration of Octreotide LAR is optional in the re-treatment period (expected very few cases), the duration of exposure to Octreotide LAR will not be calculated for the re-treatment period.

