5.4.3.1 RPSFT approach

The primary analysis of OS will be using *rank-preserving structural failure time method (RPSFT)* to correct for confounding introduced by the change of treatment (Robins and Tsiatis 1991; Korhonen et al 1999). The use of RPSFT method allows to estimate the survival time gained by anyone receiving Lutathera (i.e., either as randomized to Lutathera or after cross-over from Octreotide LAR to open-label Lutathera). The RPSFT model is based on an accelerated failure time model (Kalbfleisch and Prentice 2002) and uses a structural assumption of time-proportionality instead of a proportional hazards assumption as used in the Cox model. The widely used Cox model measures drug effect on the hazard ratio scale, whereas the accelerated failure time model measures drug effect on the survival time ratio scale.

Notation

We follow (Korhonen et al 1999) for the notation. The treatment assignment indicator is denoted by R_i and takes the value 0 if allocated to Octreotide LAR and 1 if allocated to active drug (Lutathera 10 mg). $Strata_i$ stands to baseline stratification factors. Each individual is followed from the time of randomization (DR_i) until death or the date of last contact (EOF_i) and the fixed closing date (CD_i) which ever comes first. The censoring time $C_i = \min(EOF_i - DR_i, CD_i - DR_i)$, is measured in days and is assumed to be independent of the treatment assignment. (Note: in a sensitivity analysis, censoring time $C_i = EOF_i - DR_i$ will also be considered). Time to death (T_i) is the time from randomization to death which is also measured in days. We can only observe $X_i = \min(T_i, C_i)$ with $\delta_i = 1$ if $X_i = T_i$ and $\delta_i = 0$ otherwise. Some of the subjects randomized to the Octreotide LAR arm switch to the active drug at some point after randomization. There may be several different periods when active drug has been received instead of the randomized Octreotide LAR. The total time from randomization to switch is denoted as A_i . If no switch occurs in the Octreotide LAR arm then $A_i = 0$. Switching to the active drug is potentially related to the patient's prognosis and thus cannot be assumed independent of the death time.

Thus, the observed data for each subject i are $\{R_i, Strata_i, C_i, X_i, \delta_i, A_i\}$.

Model

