For subject i , we denote U_i as the potential survival time without Lutathera. U_i is a concept that is defined for each subject at the time of the randomization and U_i may depend on the value of

the baseline risk factor. U_i will be observed only for those subjects who will never receive active drug during the study and die before $\min(EOF_i, CD_i)$.

For a given time to switch A_i , the Lutathera-free survival time U_i is linked to the death time T_i through a structural model

$$U_i = \int_0^{T_i} e^{\psi A_i(s)} ds$$

where $A_i(t) = 1$ if subject i has not switched at time t and 0 otherwise. For a fixed value of the parameter ψ the above model can be written as

$$U_i(\psi) = \int_0^{A_i} e^{\psi \times 1} ds + \int_0^{T_i - A_i} e^{\psi \times 0} ds = A_i e^\psi + (T_i - A_i).$$

If $A_i(t) = 0$ for all t then $U_i = T_i$. If, on the other hand $A_i(t) = 1$ for all t then $U_i = T_i e^\psi$. Thus the parameter ψ has the following interpretation: e^ψ expresses how much the survival time is increased or decreased on relative scale if on Lutathera versus if not on Lutathera.

Therefore, we can see that the main assumption of this method is that the total duration of survival time for each patient is the sum of two distinct parts:

- potential survival time, had no Lutathera been received, and
- time added from multiplying the duration on Lutathera by an unknown factor.

For the estimation of the parameter ψ it needs to be assumed that:

1. the above model correctly captures the drug action
2. no other factor than the amount of Lutathera received, A_i , induces a difference in survival experience for an individual i under different treatment arm assignments
3. the Lutathera-free survival time U_i for an individual i is unaffected by the drug assignment or by the survival experience of other individuals
4. the censoring time C_i is independent of the randomization mechanism R_i

Estimation algorithm for parameter ψ

Randomization guarantees that any variable measured at baseline will on average be balanced with respect to the drug assignment. In particular, $U_i \perp\!\!\!\perp R_i$ where $\perp\!\!\!\perp$ denotes statistical independence. This holds also within each of the k strata of the baseline risk factor. It follows that

$$\Pr(U_i(\psi) \leq x | R_i = 0, Strata_i = z) = \Pr(U_i(\psi) \leq x | R_i = 1, Strata_i = z), \quad z = 1, 2, \dots, k.$$

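### SAP 5.4.3.1 rescales time before the switch instead of time on Lutathera, no re-treatment correction is specified although one is promised, and the SAP names two different primary OS analyses

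*SAP*

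**What the plan says.** Patient subscripts are dropped below. T is time from randomization to death, S is time to cross-over, A is total exposure and A(t) is the exposure indicator.

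**Exposure.** The Notation part of SAP 5.4.3.1 introduces A with "The total time from randomization to switch is denoted as" and sets A = 0 for a control who never switches. The Model part sets A(t) = 1 "if subject i has not switched at time t and 0 otherwise" and arrives at U = A·e^ψ + (T − A), where U is the survival the patient would have had without Lutathera. The same section then describes the model as "time added from multiplying the duration on Lutathera by an unknown factor". Its second assumption is that "no other factor than the amount of Lutathera received", namely A, makes survival differ between arms. It also says that e^ψ "expresses how much the survival time is increased or decreased on relative scale if on Lutathera versus if not on Lutathera".

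**Re-treatment.** SAP 2.7.1 says that RPSFT and IPCW each adjust for cross-over and for re-treatment in the Lutathera arm, and 5.4.3 repeats this. The RPSFT notation describes switching from the control arm only: "Some of the subjects randomized to the Octreotide LAR arm switch to the active drug at some point after randomization". In 5.4.3.2, IPCW uses all Lutathera-arm follow-up with every weight in that arm fixed at 1.

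**Status.** SAP 2.7.1 makes ITT the primary OS analysis. SAP 5.4.3 calls ITT supportive, and 5.4.3.1 calls RPSFT primary. Protocol 12.5.2 calls the cross-over adjustments supportive.

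**The concern.** The factor e^ψ is meant to convert time lived on Lutathera into the time that would have been lived without it. If A is time before the switch, the factor falls on the wrong segment for every crossed-over control whose death counts in the estimation. Section 5.4.3.1 also gives two definitions of A that disagree for controls who never switch, so two programmers following it could obtain different estimates.

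What is at stake is the set of cross-over-adjusted OS estimates at the final analysis, and whether they may be described as corrected for re-treatment. With two analyses labelled primary, the choice could be made after the results are known.

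**Working it through.** **1. Algebra.** Take a control who switches at S and dies at T.

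- As written (A = S): U = S·e^ψ + (T − S).
- Exposure from first dose to death (A = T − S): U = S + (T − S)·e^ψ.
- Exposure only for a period L on treatment (A = L): U = T − L + L·e^ψ.

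The written value minus the second is (T − 2S)(1 − e^ψ), and minus the third is (L − S)(1 − e^ψ). The SAP does not say which exposure definition it intends. The written form agrees with them only by coincidence, at S = T/2 or S = L. When ψ = 0 all three give U = T, so the error affects the estimate of ψ and its confidence limits, not the test of no effect.

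**2. Worked cases.** Assume T = 36 months and e^ψ = 0.667. For L, take four doses 8 weeks apart and borrow the exposure rule in SAP 2.4.1.1, where for Lutathera "the last date of exposure is defined as the last date of administration + 55 days". Then L = 3 × 56 + 55 + 1 = 224 days, and 224 / 30.4375 = 7.36 months.

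| Switch month | U as written | U, first dose to death | U, on treatment |
|---|---|---|---|
| 12 | 8 + 24 = 32 | 12 + 16 = 28 | 33.5 |
| 18 | 12 + 18 = 30 | 18 + 12 = 30 | 33.5 |
| 24 | 16 + 12 = 28 | 24 + 8 = 32 | 33.5 |

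**3. Never-switching controls.** The scalar A = 0 gives U = T. The indicator equals 1 throughout and gives U = T·e^ψ. For a death at month 20 these are 20 and 13.3 months.

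**4. Direction of e^ψ.** Under continuous Lutathera U = T·e^ψ, so survival on Lutathera relative to survival without it is T/U = e^−ψ. The SAP's reading of e^ψ is the inverse.

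**5. Effect on the estimate.** The documents give no OS or switching rates, so simulation inputs are assumptions: 10,000 control and 20,000 Lutathera patients; exponential Lutathera-free OS with median 30 months; true time ratio 1.5 acting from randomization (Lutathera arm) or from the switch (controls); censoring uniform on 48 to 70.2 months; no dropout; unstratified log-rank; the SAP's recensoring min(C, C·e^ψ). Between 24% and 66% of controls switch. Switching is independent of death in some settings and tied to it in others, since the SAP says it "cannot be assumed independent of the death time". There were 12 settings with three replicates each.

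| Definition programmed | Estimated time ratio (truth 1.5) |
|---|---|
| Lutathera time, first dose to death | 1.48 to 1.53 |
| Written scalar, median switch at 17–39% of survival | 1.31 to 1.48 |
| Written scalar, median switch at 58–79% of survival | 1.54 to 2.07 |
| Written indicator | no solution in 13 of 36 replicates; 1.39 to 6.92 in the other 23 |

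The first three rows are ranges of setting means. In the same data the written scalar gave a lower estimate than Lutathera time in all 18 early-switch replicates and a higher one in all 18 late-switch replicates.

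A second simulation used 60,000 patients, no censoring, a 36-month median and switching at 20–70% of untreated survival. With a true ratio of 1.5, Lutathera time gave 1.49 to 1.55. At 30%, 50% and 80% switching, the scalar gave 1.43, 1.40 and 1.36 and the indicator 2.72, 1.93 and 1.48.

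**6. Re-treatment.** In RPSFT, whether re-treatment time counts as exposure depends on the definition left unstated in step 1. If it counts, it is absorbed with the same factor, which does not remove its effect. The method's own closing summary claims correction for cross-over only. In IPCW, a weight of 1 and full follow-up in the Lutathera arm leave no step at which re-treatment could be handled.

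**7. Status.** SAP 2.7.1 and protocol 12.5.2 agree that ITT leads and the adjusted analyses support. SAP 5.4.3 and 5.4.3.1 reverse this. SAP Section 4 declares no change from the protocol.

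**The case against.** The strongest reply is that the intended model can be recovered. The section defines U as Lutathera-free, refers to duration on Lutathera, and has the standard closed form and limiting cases, so an experienced programmer would see a drafting slip. The indicator reading also contradicts the rule that never-switchers have A = 0, so its extreme simulation results deserve little weight. In the Lutathera arm the indicator gives the intended U = T·e^ψ; only the scalar is left undefined there. The 7.36 months comes from an exposure-summary rule that nothing links to RPSFT. If exposure runs from first dose to death, re-treatment already falls inside it.

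Size matters too. At 148 versus 74 patients (400 replicates, 30% or 60% switching, a true ratio of 1.5), the scalar reading shifted the log estimate by a median of −0.13 to +0.04, against a sampling SD of 0.22 to 0.34. All replicates solved.

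Much of this stands as a limit on consequence. It does not rescue the text. Protocol 12.5.2 defers the details to the SAP, so this section is the governing specification, and it contradicts itself. Sampling noise does not excuse a systematic shift. The IPCW gap and the conflict over the primary analysis are not answered.

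**Conclusion.** The concern holds in all three parts. The exposure term is wrong as written for crossed-over controls who die and are not recensored; censored patients enter only through the recensored time, which does not involve A. The two written definitions disagree for never-switchers, and e^ψ is interpreted in the inverse direction. The promised re-treatment correction is absent from IPCW and left undefined in RPSFT. The SAP contradicts itself, and partly the protocol, on which OS analysis is primary.

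No single direction or expected size of bias can be claimed. The algebra rests on the SAP alone, whereas the simulated figures rest on assumed OS and switching and show dependence only. At trial size the shift was below sampling error in the settings tried. OS is outside the testing hierarchy, so the PFS, ORR and time-to-deterioration tests are untouched. This should be corrected before the final OS analysis.

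**What to change.** - In SAP 5.4.3.1, define A(t) = 1 while Lutathera-exposed and 0 otherwise, and A as total Lutathera-exposed time in either arm, with A = 0 for controls who never switch. Keep U = A·e^ψ + (T − A).
- State whether exposure runs from the first cross-over dose (or from randomization in the Lutathera arm) to death, or only while on treatment. If the latter, give the rule for how long it lasts after the last dose. State whether re-treatment time counts.
- Report e^−ψ as the survival-time ratio for Lutathera versus no Lutathera.
- Either delete the re-treatment claim from 2.7.1 and 5.4.3 and say that the effect includes re-treatment, or specify the adjustment. For IPCW, one option is to censor Lutathera-arm patients at re-treatment and weight them accordingly.
- State in 2.7.1, 5.4.3 and 5.4.3.1 that ITT is the primary OS analysis and that RPSFT and IPCW are supportive.
- Correct the cross-references in 2.7.1 from Section 5.4.1 to 5.4.3.

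The cost is SAP wording and programming before the final OS analysis. No new data are needed.

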By these definitions, $C_i(\psi)$ is independent of $U_i(\psi)$ and R_i . The new censoring time $C_i(\psi)$ can be interpreted as the maximum $U_i(\psi)$ that can be calculated which is smaller than C_i no matter how long individual i is on the randomized active drug. Both $X_i(\psi)$ and $\delta_i(\psi)$ can be calculated based on observed data and furthermore $\{X_i(\psi), \delta_i(\psi)\} \sqcup R_i \mid Strata_i$. Thus the estimation can be performed by calculating $X_i(\psi)$ and $\delta_i(\psi)$ for the various values of ψ within the different strata of the baseline risk factor and proceed as described in the estimation section.

This way of dealing with censoring was introduced by [Robins and Tsiatis 1991](#). Note that some extra censoring will occur due to nature of handling the censoring times in this estimation procedure. This causes some loss of power.

Summary of the method and interpretation

Drug effect is obtained by estimating the multiplicative factor; which would be interpreted as either a relative increase or decrease in survival if one took active drug (Lutathera) compared to taking Octreotide LAR. The multiplicative factor is determined by repeatedly reconstructing the anticipated survival duration of all patients by varying degrees of the factor, until both survival curves (Lutathera arm and Octreotide LAR) can no longer be distinguished, i.e., as if all patients only received Octreotide LAR.

This method maintains the original randomized-group definitions and thus preserves the validity of between group comparison. It provides a randomization based estimate of drug effect corrected for the bias due to crossover (under the assumption that the effect is multiplicative in time). This estimate is valid even in presence of outcome dependent drug change. Of note, this method requires extra censoring (i.e., some events become censored) which impacts the precision of the drug effect estimate.

5.4.3.2 Marginal Structural Cox Proportional Hazards Model using the Inverse Probability of Censoring Weighting (IPCW)

The Marginal Structural Cox Proportional Hazards Model using the Inverse Probability of Censoring Weighting (IPCW) will also be considered ([Hernan et al 2000](#)) to account for the treatment cross-over.

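### SAP 5.4.3.1 reads the RPSFT factor e^ψ as survival on versus off Lutathera, but by its own definition of U_i it is the reciprocal; the exposure variable A_i and the interpretation must be corrected together

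*SAP*

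**What the plan says.** SAP 5.4.3.1 (RPSFT approach) contains these elements:

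- **Counterfactual time.** For subject i, "we denote U_i as the potential survival time without Lutathera".
- **Observed time.** T_i "is the time from randomization to death which is also measured in days".
- **Structural model.** U_i(ψ) = A_i·e^ψ + (T_i − A_i). Two limits follow: U_i = T_i when A_i(t) is 0 throughout, and U_i = T_i·e^ψ when A_i(t) is 1 throughout.
- **Interpretation.** e^ψ "expresses how much the survival time is increased or decreased on relative scale if on Lutathera versus if not on Lutathera". The closing summary of the method gives the multiplicative factor the same orientation, "which would be interpreted as either a relative increase or decrease in survival if one took active drug (Lutathera) compared to taking Octreotide LAR".
- **Exposure variable.** A_i is described in two incompatible ways. The notation paragraph makes it the time from randomization until the switch, and the model paragraph sets A_i(t) to 1 while the subject has not switched. Yet the second model assumption equates A_i with the quantity of drug taken ("no other factor than the amount of Lutathera received"), and the notation paragraph sets A_i to 0 for control patients who never switch.

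No sentence in the section tells the analyst to take a reciprocal before reporting.

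**The concern.** An interpretation sentence in an SAP fixes how the number will be labelled in the table. Here the label points the opposite way from the equation a few lines above it. SAP 5.4.3.1 and protocol 12.5.2 both present the RPSFT effect on a survival time ratio scale, where a reader expects a value above 1 to mean benefit.

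At stake is the direction of the cross-over-adjusted survival-time ratio and of its confidence interval. A benefit would be labelled as a shortening of survival, and the interval would carry the same wrong direction.

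**Working it through.** **1. Reproduce the SAP's closed form.** The SAP gives no numerical RPSFT result, so its algebra is what can be reproduced. Integrating exp(ψ·A(s)) over 0 to T numerically with e^ψ = 0.5 and T = 40, and comparing with A·e^ψ + (T − A):

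| A | Closed form | Integral |
|---|---|---|
| 40 | 40×0.5 + 0 = 20 | 20 |
| 15 | 15×0.5 + 25 = 32.5 | 32.5 |
| 0 | 0 + 40 = 40 | 40 |

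The closed form and both limits are correct as printed.

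**2. Solve for e^ψ.** For a patient exposed throughout, U = T·e^ψ, so e^ψ = U/T, which is survival without Lutathera over survival with it. The on/off ratio is T/U = e^(−ψ). Rearranging the general model gives T = U + A·(1 − e^ψ), so exposure adds time only if e^ψ is below 1.

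**3. Size.**

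| True on/off ratio | e^ψ | e^(−ψ) |
|---|---|---|
| 2.0 | 0.50 | 2.0 |
| 1.5 | 0.67 | 1.5 |
| 1.25 | 0.80 | 1.25 |
| 0.5 | 2.0 | 0.5 |

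**4. Check by simulation.** The estimator was the SAP's grid search on the stratified log-rank statistic, with recensoring at min(C, C·e^ψ) and A as time on Lutathera. The data are assumptions: 2:1 allocation, exponential survival, and 60% of controls who progress before death crossing over. Single runs gave:

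| n | True ratio | e^ψ (95% limits) | e^(−ψ) |
|---|---|---|---|
| 6000 | 2.0 | 0.502 (0.463 to 0.560) | 1.994 |
| 6000 | 1.5 | 0.657 (0.595 to 0.726) | 1.522 |
| 222 | 2.0 | 0.353 (0.188 to 0.719) | 2.829 |
| 222 | 1.5 | 0.619 (0.427 to 0.980) | 1.616 |

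Every interval lies below 1, so each true benefit, read as the SAP words it, would look like a clear shortening. On the on/off scale the limits are reciprocals in swapped order. The first row becomes 1/0.560 = 1.79 to 1/0.463 = 2.16.

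**5. Dependence on A_i.** Let u be Lutathera-free survival, s the switch time, and the true ratio 2.

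| Patient | T | A = time on Lutathera, e^ψ = 0.5 | A = time before Lutathera (0 in Lutathera arm), e^ψ = 2 |
|---|---|---|---|
| Lutathera arm | 2u | 2u×0.5 = u | 2u |
| Control, no switch | u | u | u×2 = 2u |
| Control, switch at s | s + 2(u − s) | s + 2(u − s)×0.5 = u | 2s + 2(u − s) = 2u |

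Both columns balance the arms, so each coding has a consistent solution, and the two solutions are reciprocals. Simulation of the second coding gave e^ψ of 2.06 in one set of runs and about 2.08 in another. But that column recovers 2u, a fully treated survival time, not survival without Lutathera.

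**6. Other literal codings.** These were run at n = 6000 with a true ratio of 2:

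- With A as time to switch, 0 for control non-switchers and full follow-up in the Lutathera arm, e^ψ was 0.554, which is biased but still below 1.
- With A(t) = 1 for anyone who has not switched, including the Lutathera arm, no ψ between −2 and 2 was compatible with the data. The smallest squared statistic was 11.19 against a threshold of 3.84. The cause is visible in the algebra: Lutathera patients and unswitched controls are scaled by the same e^ψ, so their difference cannot be removed.

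**The case against.** The best defence is that the direction of e^ψ depends on how A_i is coded. If A_i is pre-Lutathera time, with 0 in the Lutathera arm, e^ψ is the on/off ratio just as the SAP says (step 5, last column). A reader might infer that the inversion is an independent error that holds whatever A_i means. The documents do not support that, because the section mixes two codings.

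The defence does not rescue the text, however. Pre-Lutathera coding contradicts the definition of U_i, the second model assumption and the zero assigned to control non-switchers. The SAP also says U_i is observed for patients who never receive active drug and die in follow-up. Under the not-switched coding such a control would have U = T·e^ψ, which then forces e^ψ = 1. SAP 5.4.3.2, the companion weighting method, codes its own indicator as 1 when active treatment is received.

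Two smaller objections stand in part:

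- The closing summary speaks of a multiplicative factor without naming e^ψ, so it is weaker evidence than the sentence in the model paragraph.
- The simulations assume the exposure coding and the larger ones far exceed the trial's 222 patients. They confirm the algebra and add no independent evidence.

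**Conclusion.** The interpretation is wrong as written. With A_i coded as Lutathera exposure, the reported survival-time ratio and its confidence limits would be inverted, and a true doubling would appear as 0.50. This rests on two conditions: that A_i is coded as the definition of U_i requires, and that e^ψ is tabulated under the SAP's own label.

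A reader might infer that the RPSFT analysis itself is invalid, or that the survival results as a whole would reverse. Neither follows. The wording does not invert the estimate of ψ, the reconstructed U_i or any Cox hazard ratio, and SAP 2.7.1 plans a hazard ratio for all three survival approaches.

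The consequences are bounded. Protocol 12.5.2 calls the cross-over adjustment supportive. SAP 2.7.1 makes the intention-to-treat approach primary and defers RPSFT to the final analysis. Overall survival is not in the testing hierarchy (SAP 2.6.1 and 5.4.1). SAP 5.4.3.1 does call RPSFT the primary survival analysis; that separate conflict affects how much weight the factor carries, not its direction. The point should be corrected, but no confirmatory conclusion depends on it.

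**What to change.** Make both changes in one edit of SAP 5.4.3.1:

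1. **Exposure.** Define A_i as total time on Lutathera, and A_i(t) as 1 while on Lutathera and 0 otherwise. Remove the wording that makes A_i the time to switch and sets A_i(t) to 1 before it.
2. **Interpretation.** In the model paragraph and the closing summary, report e^(−ψ) as the survival-time ratio on versus off Lutathera, with limits e^(−ψ_upper) and e^(−ψ_lower). Alternatively, keep e^ψ and state that values below 1 mean longer survival on Lutathera.

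Changing only the second part is unsafe. If a programmer coded A_i as time not yet switched, with 0 in the Lutathera arm, e^(−ψ) would itself be the inverted figure.

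The cost is a few sentences of SAP text and a check that the program's A_i matches. No new data are needed, and the structural equation and recensoring rule stay as printed.
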